### III. SUBJECT SELECTION

#### a. Inclusion/Exclusion Criteria

##### Group 1

**Inclusion Criteria:** Subjects will include women 18 years and older who meet the following criteria:

## Partners Human Research Committee Detailed Protocol

1. Planning pregnancy or pregnant < 28 weeks gestation
2. Currently meet criteria for stable remission from MDD, defined as a baseline score of  $\leq 10$  on the Montgomery-Åsberg Depression Rating Scale (MADRS)
3. Current or recent treatment with an AD
4. Have elected to discontinue AD medication for pregnancy (may have already begun or completed taper)
5. Have a history of a major depressive episode/ Previous Episode of MDD, as verified using the MINI Structured Clinical Interview for DSM-5; have MDD as one of their primary diagnoses
6. Has a treating prescribing clinician for the treatment of MDD

**Exclusion Criteria:** The presence of any of the following criteria will exclude subjects from participation:

1. Current major depressive episode, as diagnosed on the MINI mood portion
2. Significant risk for self-harm or harm to others
3. Psychotic symptoms
4. Meeting criteria for a primary diagnosis of schizophrenia, an active eating disorder, dementia, delirium, or other cognitive disorder
5. Presence of an active substance and/or alcohol abuse disorder within six months prior to screening
6. Pernicious anemia or history of gastric bypass surgery
7. Seizure disorder and/or on anticonvulsant medications
8. Allergy to beeswax, soy, fish, nuts, peanuts, egg, wheat, milk, and/or shellfish
9. Non-English speaking

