Prevalence of AD Use during Pregnancy. As previously demonstrated, based on data derived from health insurance and hospital records, investigators found that ADs were prescribed to nearly 8% of all pregnant women(2). The investigators found that AD use during pregnancy increased from 2.0% of all deliveries in 1996 to 7.6% of all deliveries in 2004 and 2005, with consistently more women dispensed an AD during the first trimester of pregnancy than in either the second or the third trimester. Clinicians must weigh the morbidity associated with depressive relapse and recurrence in the mother against the risk of adverse birth outcomes that may be associated with medication exposure for the fetus. In order to avoid fetal exposure to ADs where attendant risks of in utero exposure is incompletely delineated, many women discontinue these medicines regardless of risk for recurrence.

High Risk of Relapse of Depression during Pregnancy among Women who Discontinue Maintenance AD Therapy. Studies conducted over the last decade have demonstrated that prevalence of depression during pregnancy is similar to age-matched non-pregnant women, replacing previously held ideas that pregnancy was protective against psychiatric illness. Left untreated, depression can negatively impact both the mother and the fetus. For women with histories of MDD who discontinue AD medication to avoid fetal drug exposure, the risk of depressive relapse is high. In a multi-site NIMH funded collaborative study, the rate of depressive relapse among women with a history of MDD who discontinued ADs (68%) was significantly higher than the rate (26%) for women who maintained AD treatment(3). In this study, continued AD treatment during pregnancy significantly reduced the risk of maternal depressive relapse. Data from this large scale, multi-site study also demonstrated that there is a broad distribution of AD use early in pregnancy that is not wholly determined by severity of illness as defined by number of episodes of MDD. In fact, there was no association between the decision to discontinue medication during pregnancy and duration of illness, number of previous episodes, or frequency of co-morbid psychiatric illness.

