As a group, clinicians at the MGH Center for Women's Mental Health (CWMH) have extensive experience over the last 25 years providing these consultations to women presenting for the most current information regarding both risks of AD exposure during pregnancy and risks of recurrence of underlying disorder in the setting of AD discontinuation either while planning to conceive or during pregnancy. This group, under the direction of [name], has a longstanding record of recruiting women for federally funded studies of depression before, during and after pregnancy derived from a potential subject pool of 900 pregravid women per year who are seen for consultation regarding the risks of psychotropic use during pregnancy. Approximately half (450) of these women are euthymic on maintenance AD therapy and are referred by their community clinicians for consultation about maintaining, changing, or discontinuing their medication for pregnancy.

During consultations by perinatal psychiatrists, the relative risks of fetal exposure to ADs are explained, as are the attendant risks of relapse/recurrence of depression in the setting of AD discontinuation. Information about the relative risks of various treatment options is provided to both the patient and the referring clinician; referring psychiatrists are contacted both by phone and in writing. Available information informing patient decisions about treatment options and the associated risk/benefit analysis is also available to patients/potential subjects through a web driven Perinatal Information Resource Center ([www.womensmentalhealth.org](http://www.womensmentalhealth.org)), run by the MGH Perinatal and Reproductive Psychiatry Program. Patients and clinicians are consistently referred to this dynamic website, which is constantly updated with the most recent data.

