### IV. SUBJECT ENROLLMENT

#### a. Methods of enrollment

Potential subjects will be recruited from the Massachusetts General Hospital (MGH) Center for Women's Mental Health (CWMH) clinic, outpatient Obstetrics clinic, and from referrals from health care providers in the community. Interested potential participants will be referred to study staff for a pre-screening phone call. Patients potentially eligible for Group 1 will continue on in the screening process only if the patient explicitly states that she has decided to discontinue antidepressant treatment in the context of pregnancy (planning or during). Patients potentially eligible for group 2 will only continue the screening process if they state that they do not wish to start therapy with an antidepressant medication.

After a preliminary phone screening, a research coordinator working within the CWMH will schedule the patient for a baseline visit. This baseline visit will be conducted by either the principal investigator (PI) or another clinician trained in all study assessment procedures, along with trained clinical research coordinators. After an explanation of the study procedures, written informed consent will be obtained from patients prior to execution of any study assessments or procedures.

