## V. BIOSTATISTICAL ANALYSIS

We will compare the rates of depressive relapse and duration of time out of a depressive episode for Group 1 participants, and compare these data to historical controls that were also assessed prospectively. For Group 2, we will compare depressive response rates (response defined as 50% reduction in depressive symptoms on the MADRS, our primary outcome) to response rates in studies of SSRIs for the treatment of depression.

In addition, we will monitor depressive symptom burden with continuous variables across the treatment study for both groups.

To control for prenatal vitamin (PNV) use, we will supply a standard PNV to each participant to take daily in combination with EnBrace. The Sponsor has offered to supply the PNV, such that each participant will take the same PNV; this will lower the risk of inconsistencies between participants. In the statistical analysis, the data collected in this preliminary study will be compared to historical controls with a history of MDD who discontinued AD maintenance therapy during pregnancy, most of which were taking standard PNVs, but not EnBrace. This reference will allow us to estimate the relative efficacy of EnBrace in relapse prevention of women who discontinue maintenance ADs for pregnancy.

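### Group 1 may enter while still on or tapering an antidepressant, yet the whole group is compared with women who had discontinued, with no time origin, stop date or use of antidepressant status

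*Combined protocol and SAP*

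**What the plan says.** **Entry.** Group 1 inclusion criterion 3 (Section III.a) is "Current or recent treatment with an AD", with recent left undefined. Criterion 4 is "Have elected to discontinue AD medication for pregnancy (may have already begun or completed taper". Beginning or finishing the taper is allowed but not required. Section IV.a continues screening "only if the patient explicitly states that she has decided to discontinue antidepressant treatment", so the gate is a decision and not the act of stopping.

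**Comparison.** Section V sets Group 1 as a whole against "historical controls with a history of MDD who discontinued AD maintenance therapy during pregnancy". It names relapse rate and time out of a depressive episode, but not the point from which time is counted. The one factor it controls is prenatal vitamin use: "To control for prenatal vitamin (PNV) use, we will supply a standard PNV to each participant". Of the comparison it says "This reference will allow us to estimate the relative efficacy of EnBrace in relapse prevention".

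**Data capture.** The Schedule of Assessments covers weeks 0 to 12. Medical and psychiatric history is marked at V1 only, and no row concerns antidepressant use at V2 to V7. Drop criterion 2 removes a Group 1 woman who restarts an antidepressant while well. No section asks for the date of the last dose.

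**Benchmark.** Section I.b, on relapse among women who discontinue, reports that the rate among women "who discontinued ADs (68%) was significantly higher than the rate (26%) for women who maintained AD treatment". Specific Aim 1a repeats 68%. The later Section I.b text on treatment decisions gives a figure of over 43% under the same citation.

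**The concern.** Hypothesis 1a says relapse on EnBrace will be lower than in historical controls. By the protocol's own evidence, antidepressant status is strongly related to relapse. If part of Group 1's follow-up is spent under antidepressant cover and is then set against women described as having discontinued, protection from the antidepressant can be credited to EnBrace. A larger sample would not remove that error, and stop dates that were never collected may be hard to recover. Section II says the data will feed the design of a randomized trial, so an inflated impression of benefit would carry forward.

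**Working it through.** The plan gives no calculation for N=10 and no test, so there is no figure to reproduce. The check asks how far covered follow-up could move relapse if EnBrace did nothing.

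**Inputs from the documents:** 68% relapse off and 26% on an antidepressant (Section I.b); 12 weeks of follow-up (Schedule of Assessments); 10 women (Aim 1a).

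**Assumptions:**
- Historical rates accrued over 40 weeks; the length is not given.
- Half of off-antidepressant relapses fall within 13 weeks of stopping. This is suggested by the Section I.b remark that over half were in the first trimester. That remark is pregnancy timing attached to the 43% figure, so the reading is an assumption.
- A fraction f of Group 1 is covered for the first c weeks.

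**Hazard ratio, off versus on.** With equal follow-up and proportional hazards it is ln(0.32)/ln(0.74) = 3.78. The model below front-loads only the off-antidepressant hazard, so it uses [−ln(0.66)/13]/[−ln(0.74)/40] = 0.03196/0.00753 = about 4.2, where 0.66 = 1 − 0.5 × 0.68.

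**One woman's 12-week risk, covered for c weeks:** 1 − 0.74^(c/40) × 0.66^((12−c)/13)
- c = 0: 31.9%
- c = 4: 24.9%
- c = 6: 21.1%

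**Group average:** (1 − f) × 31.9% + f × risk(c)

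| Share covered | 4 weeks | 6 weeks |
|---|---|---|
| 25% | 30.1% | 29.2% |
| 50% | 28.4% | 26.5% |
| 75% | 26.6% | 23.8% |

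For half covered, the drop from 31.9% is 0.35 women in ten at 4 weeks and 0.54 at 6 weeks.

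**Sensitivity, half covered for 4 or 6 weeks:**
- Historical follow-up of 30 weeks: 28.7%, 27.1%; of 52 weeks: 28.1%, 26.1%.
- Constant hazard over 40 weeks: 29.0% uncovered, falling to 25.8%, 24.2%.
- 43% in place of 68% (0.785 in place of 0.66): 20.0% uncovered, falling to 18.2%, 17.3%.

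The direction is the same throughout. Both sides use 12 weeks, so the gap between 12 weeks and the historical follow-up length is not counted here.

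**The case against.** The strongest reply is that the mismatch depends on a source the documents do not describe closely enough. Section V says the controls discontinued and were assessed prospectively; it does not say they were off treatment at time zero. If they too were followed through taper, the comparison is closer to like with like. This stands: the bias is conditional.

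Four stronger readings are tempting, and the documents do not support them.

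- **That antidepressant use goes unrecorded after V1.** The schedule is not a full list of data collected. It has no adverse-event row, yet Section VIII records adverse events at each visit, and drop criteria 2 and 3 require staff to learn of some antidepressant changes. What can be said is that no stop date is called for and Section V makes no use of antidepressant status.
- **That about half of Group 1 will enter covered.** Section III.b says "Approximately half (450) of these women are euthymic on maintenance AD therapy", but this describes the consultation pool before any decision, and the clinic is only one route of recruitment. It makes covered entry foreseeable and gives no proportion.
- **That the distortion exceeds one woman in ten.** Full 12-week cover gives a risk of 8.6% per woman, and so a drop of 1.2 women in ten if half are covered and 1.7 if three-quarters are. Those figures need women who have decided to stop to remain covered throughout.
- **That Hypothesis 1a should rest on off-antidepressant follow-up alone.** That would drop women who relapse during taper and keep those who stayed well long enough to stop, which can itself favour EnBrace. Aim 1a concerns women who have decided to stop, so a whole-group result is legitimate if it is labelled for what it is.

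It is also fair to say that this is a ten-woman pilot with no stated test. The exact 95% interval for 2 relapses in 10 is 2.5% to 55.6%, far wider than the shift computed. In this model the difference in follow-up length (about 32% at 12 weeks against 68%) is larger, but it is a separate matter. Small numbers do not excuse a comparison that cannot separate the product from the antidepressant.

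**Conclusion.** The point holds as a weakness of design and analysis that should be corrected. As written, the plan can credit EnBrace with antidepressant protection, because entry status is mixed, the comparator is women who discontinued, no time origin is stated and no stop date is required. The direction favours EnBrace unless the historical women were also followed from before they stopped. Half of Group 1 covered for 4 to 6 weeks would lower expected 12-week relapse by about 3.5 to 5.4 percentage points with no product effect. That figure rests on an assumed historical follow-up, relapse timing, entry mix and length of cover, so it is illustrative and not an estimate of the bias.

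**What to change.** - Record the date of the last antidepressant dose at V1, and update antidepressant status with dates at each visit.
- State the time origin for relapse and for time out of episode.
- Keep the whole-group result, count every relapse including those during taper, and describe it as a mixed on- and off-antidepressant population.
- Add an off-antidepressant analysis beside it. Where the historical data include stop dates, count time from last dose with delayed entry at enrolment. Otherwise start at V1 or the later stop date and state the mismatch. Show relapses on an antidepressant or during taper separately, and note that this analysis selects women who stayed well until they stopped.
- Do not attribute a whole-group difference from the discontinuation benchmark to EnBrace unless the off-antidepressant result agrees.
- Reconcile 68% with the figure of over 43% under the same citation before naming the benchmark.

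**Cost.** A few data fields and a smaller, less precise secondary analysis. Of 10 × 12 = 120 planned woman-weeks, five women covered for 4 or 6 weeks leave 120 − 20 = 100 or 120 − 30 = 90, ignoring relapse and dropout. Eligibility and clinical management are unchanged.

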### **Group 2**

**Inclusion Criteria:** Subjects will include women 18 years and older who meet the following criteria:

1. Planning pregnancy or pregnant < 28 weeks gestation
2. Currently experiencing clinically significant depressive symptoms, defined as a baseline score of  $\geq 15$  on the Montgomery-Åsberg Depression Rating Scale (MADRS)
3. Experiencing a major depressive episode, as verified using the MINI Structured Clinical Interview for DSM-5; have MDD as one of their primary diagnoses
4. Has a treating prescribing clinician for the treatment of MDD

**Exclusion Criteria:** The presence of any of the following criteria will exclude subjects from participation:

1. Significant risk for self-harm or harm to others
2. Psychotic symptoms
3. Meeting criteria for a primary diagnosis of schizophrenia, an active eating disorder, dementia, delirium, or other cognitive disorder
4. Presence of an active substance and/or alcohol abuse disorder within six months prior to screening
5. Pernicious anemia or history of gastric bypass surgery
6. Seizure disorder and/or on anticonvulsant medications
7. Allergy to beeswax, soy, fish, nuts, peanuts, egg, wheat, milk, and/or shellfish

8. Non-English speaking

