## **II. SPECIFIC AIMS**

### **a. Specify objectives and hypotheses to be tested**

**Objective:** The overarching goal of this investigation is to assess EnBrace as a treatment for the acute treatment and prevention of depression in women with a history of major depressive disorder who decide to avoid or discontinue their maintenance AD treatment for pregnancy. After completing this protocol, we plan to use the preliminary data for the development of a randomized controlled trial protocol. We will include two groups of women who are interested in minimizing medication exposures while trying to conceive or during pregnancy: 1) women who have histories of depression and are not depressed, and would like to stop antidepressants for pregnancy, 2) women in depressive episodes who are pregnant or trying to conceive (on or off of antidepressant medications).

**Specific Aim 1a:** To evaluate the efficacy of EnBrace when used as maintenance treatment for MDD in a group of women (N=10) who are trying to conceive or are early in pregnancy and who

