## Partners Human Research Committee Detailed Protocol

have decided to stop ADs (Group 1). Relapse rates for women in this context have been demonstrated to be high, with 68% relapse rates in a large multisite NIMH-funded trial.

**Specific Aim 1b:** To evaluate the efficacy of EnBrace when used as an acute treatment for MDD in a group of women (N=10) who are trying to conceive or are early in pregnancy (Group 2). Women will have major depressive episodes in this group, and may receive EnBrace as monotherapy, or as an adjunct to current pharmacotherapy.

*Hypothesis 1a:* We hypothesize that relapse rates will be lower for women who receive EnBrace compared to historical controls. MDD relapse will be determined by the Mini-International Neuropsychiatric Interview (MINI) mood module that will be administered by a study clinician at each visit.

*Hypothesis 1b:* We hypothesize that the majority of women who receive EnBrace will experience a response (50% improvement in depressive symptoms) to EnBrace therapy.

**Specific Aim 2:** To identify biological markers as potential predictors of response to EnBrace.

*Hypothesis 2:* We hypothesize that pre- to post-treatment changes in homocysteine, folate, B12, IL-6 and CRP will be associated with response to EnBrace. We hypothesize specifically that levels of folate and B12 will increase and homocysteine will decrease temporally with treatment and be predictive of prevention of depressive episodes. We hypothesize that treatment will lower IL-6 and CRP levels due to the anti-inflammatory components of EnBrace (i.e., omega-3 fatty acids) and that decreased levels of inflammatory markers may predict lower risk of depressive relapse in participants who enter the study while not on a depressive episode (Group 1), and will predict response to treatment in women who enter the study while in a depressive episode (Group 2).

**Specific Aim 3 (Exploratory):** To identify factors influencing adherence to and tolerability of treatment. This will be achieved by using qualitative methods to explore (a) perceived risks and benefits of treatment; (b) perceived side effect profile; (c) treatment convenience; (d) knowledge of, attitudes towards, and preferences for depression treatment while attempting to conceive or early pregnancy.

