**b. Recruitment Sources**

We plan to enroll 10 women who meet criteria for history of MDD, have decided to stop AD medication while trying to conceive or during early pregnancy (< 28 weeks), and are eligible to receive treatment with EnBrace prenatal supplement. We also plan to enroll 10 women who meet the criteria for a current major depressive episode who are trying to conceive or pregnant (< 28 weeks), and are eligible to receive treatment with EnBrace prenatal supplement.

Potential subjects will be enrolled from four major sources:

- 1) Women who have had a previous interaction with the MGH Center for Women's Mental Health, either through research or clinically, and have consented to be contacted about future studies for which they may be eligible.
  - a. These women will be contacted by e-mail, postal mail, and phone, based on how each indicated she would prefer to be contacted by our program.
- 2) Women who are currently seen in consults who indicate to the MGH Perinatal Psychiatrist with whom they have a consult that they would be interested in adjunct or alternative medication for pregnancy
  - a. These women will be given information about the study at the end of their consult with a Perinatal Psychiatrist and asked to schedule a separate appointment for a screening interview with a member of the study staff
- 3) Women who are seen in the MGH outpatient Obstetrics department
  - a. These women will be pre-identified through preliminary screening, and approached during their clinic visit by a provider in the Obstetrics department who will introduce the study and obtain permission to be contacted by study staff.
- 4) Physicians in the community

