### Drop criteria:

## Partners Human Research Committee Detailed Protocol

1. Participant experiences severe worsening of depression symptoms, as indicated by a CGI-I of 6 or 7 on 2 consecutive visits determined by a licensed study psychiatrist. Subjects with a CGI-I of 6 or 7 on 2 consecutive visits will be terminated from the study and referred for additional clinical treatment as needed.
2. A Group 1 participant who is not experiencing depression symptoms decides to restart antidepressant treatment while they are well
3. A Group 2 participant who enrolled during a current depressive episode has either started a new antidepressant or increased the dose of an antidepressant they were already taking
4. Emergence of suicidal ideation, homicidal ideation, or psychotic symptoms. The anchors for suicidality will include the QIDS-SR, Question 12 (with an answer of 2 or 3) and the MADRS, Question 10 (with an answer of 4, 5, or 6). Acute suicidality, based on these measures and the licensed psychiatrist's clinical assessment, will result in termination of participation in the study and swift triage to the Acute Psychiatry Service at Massachusetts General Hospital.
5. Evidence of abuse or misuse of study medication
6. Evidence of current alcohol and/or drug abuse
7. Any severe or unstable medical illness that includes concern regarding safety of continued use of study medication
8. Intolerance to study medication as determined by research clinician
9. Significant hypersensitivity reaction
10. Inability or unwillingness to complete the study procedures

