### **Protection Against Risk**

As discussed above, in order to (1) prevent patients from feeling obligated to participate in the study, subjects eligible for Group 1 will only be enrolled if they decide to discontinue AD treatment. Subjects eligible for Group 2 will only be included if they have decided not to accept treatment with an antidepressant medication (if not currently on an antidepressant) or opt not to increase the dose or add an adjunctive antidepressant medication (if presenting on an antidepressant). The risks and benefits of

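### Group 2 has no look-back on antidepressant changes before V1, so improvement after a recent start or increase counts as response to EnBrace

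*Combined protocol and SAP*

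**What the plan says.** Section III.a lists four inclusion and eight exclusion criteria for Group 2. The clinical entry conditions are a baseline MADRS of at least 15 and "Experiencing a major depressive episode, as verified using the MINI Structured Clinical Interview for DSM-5; have MDD as one of their primary diagnoses". No criterion mentions a recent start, dose change or stop of an antidepressant.

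Mixed antidepressant status is intended. The objective in section II describes Group 2 as "women in depressive episodes who are pregnant or trying to conceive (on or off of antidepressant medications"), and Specific Aim 1b says that participants "may receive EnBrace as monotherapy, or as an adjunct to current pharmacotherapy".

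Three places restrict antidepressant changes:
- Section IV.a (Methods of enrollment): at the phone screen, a Group 2 candidate continues only if she does not wish to start an antidepressant.
- Section VI, Protection Against Risk: a woman already treated must "opt not to increase the dose or add an adjunctive antidepressant medication (if presenting on an antidepressant").
- Drop criteria, item 3: an enrolled Group 2 woman is dropped if she "has either started a new antidepressant or increased the dose of an antidepressant they were already taking".

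Section V (Biostatistical Analysis) defines response as a 50% reduction on the MADRS, names it the primary outcome, and compares the Group 2 rate with response rates from SSRI studies. It has no analysis by antidepressant status or recent change. The schedule of assessments takes medical and psychiatric history at V1 but has no line for concomitant medication and no field for the date of the last antidepressant change.

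**The concern.** Drop criterion 3 shows that the protocol regards a new or increased antidepressant as incompatible with judging EnBrace in Group 2. It applies that judgement only after enrolment. A woman who makes the same change shortly before V1 enters, stays for 12 weeks while that change may still be taking effect, and is scored as an EnBrace responder if her MADRS halves. There is no control group and Group 2 has 10 places, so one or two such women can matter to whether a majority respond. Section II says the data will be used to develop a randomized trial, so an inflated or blurred response rate would carry into that design.

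**Working it through.** **Text check.** The question is whether any rule covers the time before V1.

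| Place | Rule | Covers a change made before V1? |
|---|---|---|
| III.a, Group 2 criteria | Current episode on the MINI, MADRS at least 15, exclusions | No |
| IV.a, phone screen | Does not wish to start an antidepressant | No; concerns future intent |
| VI, Protection Against Risk | Opts not to increase or add, if already on one | No; a woman who started last week is already on one and qualifies |
| Drop criterion 3 | New antidepressant or increased dose | No; applies to enrolled women, and omits stops and reductions |
| V, analysis | 50% MADRS reduction counts as response | No separation by recent change |

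Section III.b adds a contradiction. It describes Group 2 women at enrolment as having decided to begin antidepressant monotherapy or to supplement their current antidepressant. That does not agree with section IV.a or with Protection Against Risk.

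**Size.** The plan gives no reference response rate, error rate or power for Group 2, so there is no figure of its own to reproduce. The following is an illustration.

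Inputs from the documents: n = 10 (section III.b: "We also plan to enroll 10 women who meet the criteria for a current major depressive episode"); Hypothesis 1b expects a majority to respond, read here as at least 6 of 10.

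Assumed inputs: response of 40% on a settled regimen; k recent changers, responding at rate q.

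Formula: P(X >= 6), where X = Binomial(10 - k, 0.40) + Binomial(k, q), independent.

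- k = 0: P = 0.166.
- k = 1: P = P(at least 6 of 9) + q x P(exactly 5 of 9) = 0.0994 + 0.1672q. At q = 0.50 this is 0.183; at q = 0.70 it is 0.216.
- k = 3: for the seven settled women, P(at least 6, 5, 4, 3) = 0.0188, 0.0963, 0.2898, 0.5801. These are weighted by the chance of 0, 1, 2, 3 responders among the three changers. At q = 0.50 the weights are 0.125, 0.375, 0.375, 0.125, giving 0.0024 + 0.0361 + 0.1087 + 0.0725 = 0.220. At q = 0.70 the result is 0.345.
- k = 3 with changers who do worse: q = 0.20 gives 0.079 and q = 0.30 gives 0.119.

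| Recent changers | Their response | Chance of at least 6 of 10 |
|---|---|---|
| 0 | - | 17% |
| 1 | 50-70% | 18-22% |
| 3 | 50-70% | 22-35% |
| 3 | 20-30% | 8-12% |

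If settled response is 30% instead, the chance is 5% with no changers and 10-18% with three responding at 50-70%. For context, 6 of 10 has an exact 95% interval of 26% to 88%.

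**The case against.** The strongest reply is that Group 2 consists of women who want to minimise medication exposure and have declined to start or increase an antidepressant. A woman who did so days earlier is possible but is not the woman being sought, and the documents give no basis for three in ten, or for any other number. With only one, the shift is 1 to 5 percentage points. The study is also an uncontrolled pilot with no formal test of Hypothesis 1b. Even with no recent changers, a majority arises 17% of the time under the 40% assumption, so small numbers and the lack of a control are problems regardless. All of this stands. It limits the size of the point but does not close the gap in the text.

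A reader might infer stronger versions that the documents do not support:
- *Every recent change, including a stop, would remove a woman if made after V1.* Drop criterion 3 names only a new antidepressant or an increased dose, so the inconsistency around V1 holds for starts and increases alone.
- *Every recent change inflates response.* A recent stop may worsen depression and lower response, or may raise the baseline score through transient symptoms and so increase apparent response. The documents do not settle which.
- *Nothing could separate the earlier change from EnBrace.* Reporting women without a recent change separately does so in part, provided the dates are collected.
- *An entry window is needed and costs little because the clinic sees 900 women a year.* Section III.b describes those as pregravid women consulting about psychotropics, about half of them euthymic on maintenance treatment. That is not a count of the Group 2 pool. A waiting period could also carry some pregnant women past the limit of 28 weeks' gestation.

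**Conclusion.** The point holds in a limited form. Nothing in the plan looks back before V1, so a recent starter or increaser is eligible and her 50% MADRS reduction is attributed to EnBrace, although the plan would drop her for the same change after V1. That part rests on the text and is firm. Recent stops and reductions also confound the estimate, in an unknown direction, and no rule covers them on either side of V1. The impact is uncertain: the frequency of recent changes is unknown, and the probabilities above depend on assumed response rates and on reading a majority as 6 of 10. It merits correction because the remedy is cheap and has to be in place when data collection starts.

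**What to change.** 1. At V1, record the date and type (start, increase, reduction, stop) of the last antidepressant change.
2. In section V, prespecify a look-back period, its length set by the investigators before enrolment. Report the Hypothesis 1b response rate in women with no change in that period as the main figure, with the all-enrolled rate and the recent changers shown beside it.
3. Reconcile the description of the Group 2 decision in section III.b with section IV.a and Protection Against Risk.

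The cost is one data field and a smaller denominator for the main figure: with three recent changers it would rest on 10 - 3 = 7 women, and its interval would be wider. No one is delayed or excluded, and no one's treatment changes. Restricting entry to women with no recent change is an option for the sponsor, not a requirement of this point.
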